	14.3.1.8.1.1	Treatment-Emergent Adverse Events Leading to Study Withdrawal by System Organ Class and Preferred Term – Stage 1	Stage 1 Safety Set

This document is confidential.

Header	Table Number	Name	Analysis Set
	14.3.1.8.1.2	Ocular Treatment-Emergent Adverse Events Leading to Study Withdrawal by System Organ Class and Preferred Term – Stage 1	Stage 1 Safety Set
	14.3.1.8.1.3	Non-Ocular Treatment-Emergent Adverse Events Leading to Study Withdrawal by System Organ Class and Preferred Term – Stage 1	Stage 1 Safety Set
	14.3.1.8.2.1	Treatment-Emergent Adverse Events Leading to Study Withdrawal by System Organ Class and Preferred Term – Stage 2	Stage 2 Safety Set
	14.3.1.8.2.2	Ocular Treatment-Emergent Adverse Events Leading to Study Withdrawal by System Organ Class and Preferred Term – Stage 2	Stage 2 Safety Set
	14.3.1.8.2.3	Non-Ocular Treatment-Emergent Adverse Events Leading to Study Withdrawal by System Organ Class and Preferred Term – Stage 2	Stage 2 Safety Set
	14.3.1.9.1.1	Treatment-Emergent Adverse Events Leading to Permanent Discontinuation of Study Drug by System Organ Class and Preferred Term – Stage 1	Stage 1 Safety Set
	14.3.1.9.1.2	Ocular Treatment-Emergent Adverse Events Leading to Permanent Discontinuation of Study Drug by System Organ Class and Preferred Term – Stage 1	Stage 1 Safety Set
	14.3.1.9.1.3	Non-Ocular Treatment-Emergent Adverse Events Leading to Permanent Discontinuation of Study Drug by System Organ Class and Preferred Term – Stage 1	Stage 1 Safety Set
	14.3.1.9.2.1	Treatment-Emergent Adverse Events Leading to Permanent Discontinuation of Study Drug by System Organ Class and Preferred Term – Stage 2	Stage 2 Safety Set
	14.3.1.9.2.2	Ocular Treatment-Emergent Adverse Events Leading to Permanent Discontinuation of Study Drug by System Organ Class and Preferred Term – Stage 2	Stage 2 Safety Set
	14.3.1.9.2.3	Non-Ocular Treatment-Emergent Adverse Events Leading to Permanent Discontinuation of Study Drug by System Organ Class and Preferred Term – Stage 2	Stage 2 Safety Set
	14.3.1.10.1.1	Treatment-Emergent Adverse Events Leading to Death by System Organ Class and Preferred Term – Stage 1	Stage 1 Safety Set
	14.3.1.10.1.2	Ocular Treatment-Emergent Adverse Events Leading to Death by System Organ Class and Preferred Term – Stage 1	Stage 1 Safety Set
	14.3.1.10.1.3	Non-Ocular Treatment-Emergent Adverse Events Leading to Death by System Organ Class and Preferred Term – Stage 1	Stage 1 Safety Set

This document is confidential.

Header	Table Number	Name	Analysis Set
	14.3.1.10.2.1	Treatment-Emergent Adverse Events Leading to Death by System Organ Class and Preferred Term – Stage 2	Stage 2 Safety Set
	14.3.1.10.2.2	Ocular Treatment-Emergent Adverse Events Leading to Death by System Organ Class and Preferred Term – Stage 2	Stage 2 Safety Set
	14.3.1.10.2.3	Non-Ocular Treatment-Emergent Adverse Events Leading to Death by System Organ Class and Preferred Term – Stage 2	Stage 2 Safety Set
	14.3.1.11.1.1	Treatment-Emergent Adverse Events Associated with Antimuscarinic Function by System Organ Class and Preferred Term – Stage 1	Stage 1 Safety Set
	14.3.1.11.1.2	Ocular Treatment-Emergent Adverse Events Associated with Antimuscarinic Function by System Organ Class and Preferred Term – Stage 1	Stage 1 Safety Set
	14.3.1.11.1.3	Non-Ocular Treatment-Emergent Adverse Events Associated with Antimuscarinic Function by System Organ Class and Preferred Term – Stage 1	Stage 1 Safety Set
	14.3.1.11.2.1	Treatment-Emergent Adverse Events Associated with Antimuscarinic Function by System Organ Class and Preferred Term – Stage 2	Stage 2 Safety Set
	14.3.1.11.2.2	Ocular Treatment-Emergent Adverse Events Associated with Antimuscarinic Function by System Organ Class and Preferred Term – Stage 2	Stage 2 Safety Set
	14.3.1.11.2.3	Non-Ocular Treatment-Emergent Adverse Events Associated with Antimuscarinic Function by System Organ Class and Preferred Term – Stage 2	Stage 2 Safety Set
	14.3.1.12.1.1	Treatment-Emergent Adverse Events by System Organ Class, Preferred Term, and Sex – Stage 1	Stage 1 Safety Set
	14.3.1.12.1.2	Ocular Treatment-Emergent Adverse Events by System Organ Class, Preferred Term, and Sex – Stage 1	Stage 1 Safety Set
	14.3.1.12.1.3	Non-Ocular Treatment-Emergent Adverse Events by System Organ Class, Preferred Term, and Sex – Stage 1	Stage 1 Safety Set
	14.3.1.12.2.1	Treatment-Emergent Adverse Events by System Organ Class, Preferred Term, and Sex – Stage 2	Stage 2 Safety Set
	14.3.1.12.2.2	Ocular Treatment-Emergent Adverse Events by System Organ Class, Preferred Term, and Sex – Stage 2	Stage 2 Safety Set
	14.3.1.12.2.3	Non-Ocular Treatment-Emergent Adverse Events by System Organ Class, Preferred Term, and Sex – Stage 2	Stage 2 Safety Set

This document is confidential.

Header	Table Number	Name	Analysis Set
	14.3.1.13.1.1	Treatment-Emergent Adverse Events by System Organ Class, Preferred Term, and Race – Stage 1	Stage 1 Safety Set
	14.3.1.13.1.2	Ocular Treatment-Emergent Adverse Events by System Organ Class, Preferred Term, and Race – Stage 1	Stage 1 Safety Set
	14.3.1.13.1.3	Non-Ocular Treatment-Emergent Adverse Events by System Organ Class, Preferred Term, and Race – Stage 1	Stage 1 Safety Set
	14.3.1.13.2.1	Treatment-Emergent Adverse Events by System Organ Class, Preferred Term, and Race – Stage 2	Stage 2 Safety Set
	14.3.1.13.2.2	Ocular Treatment-Emergent Adverse Events by System Organ Class, Preferred Term, and Race – Stage 2	Stage 2 Safety Set
	14.3.1.13.2.3	Non-Ocular Treatment-Emergent Adverse Events by System Organ Class, Preferred Term, and Race – Stage 2	Stage 2 Safety Set
	14.3.1.14.1.1	Treatment-Emergent Adverse Events by System Organ Class, Preferred Term, and Age – Stage 1	Stage 1 Safety Set
	14.3.1.14.1.2	Ocular Treatment-Emergent Adverse Events by System Organ Class, Preferred Term, and Age – Stage 1	Stage 1 Safety Set
	14.3.1.14.1.3	Non-Ocular Treatment-Emergent Adverse Events by System Organ Class, Preferred Term, and Age – Stage 1	Stage 1 Safety Set
	14.3.1.14.2.1	Treatment-Emergent Adverse Events by System Organ Class, Preferred Term, and Age – Stage 2	Stage 2 Safety Set
	14.3.1.14.2.2	Ocular Treatment-Emergent Adverse Events by System Organ Class, Preferred Term, and Age – Stage 2	Stage 2 Safety Set
	14.3.1.14.2.3	Non-Ocular Treatment-Emergent Adverse Events by System Organ Class, Preferred Term, and Age – Stage 2	Stage 2 Safety Set
14.3.2		Listings of Deaths, Other Serious, and Significant Adverse Events	
	14.3.2.1	Listing of Deaths	Safety Set
	14.3.2.2.1	Listing of Serious Ocular Treatment-Emergent Adverse Events	Safety Set
	14.3.2.2.2	Listing of Serious Non-Ocular Treatment-Emergent Adverse Events	Safety Set
	14.3.2.3.1	Listing of Treatment-Emergent Adverse Events Leading to Permanent Discontinuation of Study Drug	Safety Set
	14.3.2.3.2	Listing of Ocular Treatment-Emergent Adverse Events Leading to Permanent Discontinuation of Study Drug	Safety Set
	14.3.2.3.3	Listing of Non-Ocular Treatment-Emergent Adverse Events Leading to Permanent Discontinuation of Study Drug	Safety Set

This document is confidential.

Header	Table Number	Name	Analysis Set
	14.3.2.4.1	Listing of Treatment-Emergent Adverse Events Leading to Withdrawal from Study	Safety Set
	14.3.2.4.2	Listing of Ocular Treatment-Emergent Adverse Events Leading to Withdrawal from Study	Safety Set
	14.3.2.4.3	Listing of Non-Ocular Treatment-Emergent Adverse Events Leading to Withdrawal from Study	Safety Set
14.3.3	Not to be used for any Tables	Narratives of Deaths, Other Serious, and Certain Other Significant Adverse Events ( NOTE: this section is for Medical Writing narratives only, normally not completed by Syneos Health Biostatistics. No tables should go here. ).	
14.3.4		Abnormal Laboratory Value (each subject)	
14.3.4.1		Ophthalmic Safety Assessment Data	
	14.3.4.1.1.1	Monocular Best-Corrected Visual Acuity Results – Stage 1	Stage 1 Safety Set
	14.3.4.1.1.2	Monocular Best-Corrected Visual Acuity Results – Stage 2	Stage 2 Safety Set
	14.3.4.1.2.1	Pupil Size (mm) – Stage 1	Stage 1 Safety Set
	14.3.4.1.2.2	Pupil Size (mm) – Stage 2	Stage 2 Safety Set
	14.3.4.1.3.1	Slit Lamp Examination Results – Stage 1	Stage 1 Safety Set
	14.3.4.1.3.2	Slit Lamp Examination Results – Stage 2	Stage 2 Safety Set
	14.3.4.1.4.1	Dilated Fundus Examination Results – Stage 1	Stage 1 Safety Set
	14.3.4.1.4.2	Dilated Fundus Examination Results – Stage 2	Stage 2 Safety Set
	14.3.4.1.5.1	Tonometry - Intraocular Pressure (mmHg) – Stage 1	Stage 1 Safety Set
	14.3.4.1.5.2	Tonometry - Intraocular Pressure (mmHg) – Stage 2	Stage 2 Safety Set
14.3.4.2		Vital Signs and Physical Findings	
	14.3.4.2.1	Vital Signs and Physical Findings – Stage 1	Stage 1 Safety Set
	14.3.4.2.2	Vital Signs and Physical Findings – Stage 2	Stage 2 Safety Set
14.3.4.3		Quality of Life	
	14.3.4.3.1	Modified Amblyopia Treatment Index (mATI)	Stage 2 Safety Set

This document is confidential.

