The drop-out rate over the 3 years of the safety and efficacy stage of the study (Stage 1) is estimated to be 27% ( $\sim$ 10% per year). As long as this drop-out rate is not exceeded, then at least 150 subjects (300 eyes) receiving the higher concentration (0.02% atropine) will be available for the evaluation of safety.

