# Withdrawal of Subjects:

All subjects randomized into the study will be encouraged to complete all study assessments through the Month 48 Visit (End of Study), including subjects that cannot or do not wish to continue study treatment (withdraw consent/assent from study treatment but are willing to continue study visits).

The following are the criteria for considering withdrawal from the study (Study discontinuation prior to Visit Month 48):

- Withdrawal of subject consent/assent to continue with study visits.
- If the site and/or the overall study is terminated for any reason.
- The Investigator considers it is in the best interest for the subject to leave the study. This may include the development of damage to the cornea (Section 8.5 Discontinuation of Study Medication).

If a subject withdraws from the study, the reason for the subject's withdrawal will be recorded in the electronic case report form (eCRF).

If a subject is discontinued from study medication before the Month 48 visit, then all Month 48 procedures should be performed at the visit the subject discontinues study medication. The subject should continue in the study off study medication. Subjects should be encouraged to return for the 6 Month interval visits; however, returning for the 12 Month interval visits is essential. Subjects discontinuing study medication prior to Month 36 would continue to be seen for scheduled visits (at 6 Month or 12 Month intervals as noted above) until they reach the Month 36 interval.

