### 6.2. Key Definitions

Treatment-emergent adverse events (TEAEs) of Stage 1 are defined as any new or worsening of existing adverse events that occur or worsen between the first dose date of Stage 1 and the last dose date of Stage 1.

TEAEs of Stage 2 are defined as any AE the occurs or worsens between the first dose date of Stage 2 and the last dose date of Stage 2.

First dose date for Stage 1 is defined as the first dose of study medication received after randomization in Stage 1.

First dose date for Stage 2 is defined as the first dose of study medication received after the Stage 1 last dose date and subject is re-randomized.

For subjects who did not receive study medication in a given stage, leave first dose date for that stage as missing. If the first dose date is missing and if the subject is randomized, impute the missing first dose date using the randomization date in the analysis of Time to Change from Baseline in Myopia Progression of -0.75D (see 8.3.7 and 8.3.8).

Baseline for Stage 1 is defined as the last measurement prior to first dose of study medication in Stage 1, If an adverse event starts or non-study medication taken on the day of first dose it will be treated as occurring after treatment started. All other planned measurements are presumed to occur prior to first dose of study medication.

Baseline for Stage 2 will be defined as latest results prior to start of study medication in Stage 2, which occurs the day after the Month 36 visit. The results of the Month 36 visit will act as the baseline for Stage 2.

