### 9.1. Extent of Exposure

Duration of exposure will be summarized using descriptive statistics by treatment group for each stage. The duration of exposure will also be categorized (<6, 6-<12, 12-<18, 18-<24, 24-<30, 30-<36, ≥36 months for Stage 1; <3, 3-<6, 6-<9, 9-<12, ≥12 months for Stage 2), and tabulated by treatment group. Duration of exposure (months) will be calculated as  $((\text{Date of Last Dose} - \text{Date of First Dose}) + 1) / 30.4375$ . If date of last dose is unknown, then the date of last clinical visit will be used.

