### 9.3. Adverse Events

The analysis of AEs will be based on the concept of treatment-emergent AEs (TEAEs). An adverse event is any untoward medical occurrence associated with the use of a drug in humans, whether or not considered drug-related.

Treatment-emergent adverse events (TEAEs) of Stage 1 are defined as any new or worsening of existing adverse events that occur or worsen between start (or increase in intensity on or after the first dose date

This document is confidential.

of Stage 1 treatment on day 1) and the last dose date of Stage 1. TEAEs of Stage 2 are defined as any AE that occurs or worsens between the first dose date of Stage 2 and the last dose date of Stage 2.

The first dose date for Stage 1 is defined as the first dose of study medication received after randomization in Stage 1. The first dose date for Stage 2 is defined as the first dose of study medication received after the Stage 1 last dose date and subject is re-randomized. All adverse events (AEs) will be coded using the MedDRA version 20.1 or higher. The following listings of AEs will be provided by Stage and subjects:

- All AEs,
- Serious adverse events (SAEs) Serious ocular and non-ocular AEs, respectively
- All deaths
- TEAEs (overall, ocular, non-ocular, respectively) leading to study withdrawal
- TEAEs (overall, ocular, non-ocular, respectively) leading to study drug discontinuation
- Severe AEs
- Study drug related AEs
- Study drug related SAEs

Treatment-emergent adverse events will be included in summary tables by treatment received for each stage. Ocular TEAEs will be summarized separately from all other TEAEs. An overall summary table of TEAEs for each stage will be produced for the following categories:

- Any Ocular TEAE
- Severe Ocular TEAEs
- Study drug-related Ocular TEAEs
- Serious Ocular TEAEs
- Study drug-related Serious Ocular TEAEs
- Ocular TEAEs leading to study discontinuation
- Ocular TEAEs leading to death
- Any Non-Ocular TEAE
- Severe Non-Ocular TEAEs
- Study drug-related Non-Ocular TEAEs
- Serious Non-Ocular TEAEs
- Study drug-related Serious Non-Ocular TEAEs
- Non-Ocular TEAEs leading to study discontinuation
- Non-Ocular TEAEs leading to death

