All TEAEs will be classified by System Organ Class (SOC) and Preferred Term (PT). Frequency count of TEAEs, the number of unique subjects experiencing a TEAE, percentage of unique subjects experiencing a TEAE, and total number of events will be tabulated by treatment and Stage for ocular and other TEAEs separately. For the number of unique subjects reporting, if a subject reported more than one TEAE that was coded to the same SOC or PT, the subject will be counted only once for that specific SOC or PT.

The following summaries of TEAEs will also be provided:

- TEAEs by SOC and PT
- Ocular TEAEs by SOC and PT
- Non-Ocular TEAEs by SOC and PT

This document is confidential.

- TEAEs by SOC, PT, and maximum severity
- Ocular TEAEs by SOC, PT, and maximum severity
- Non-Ocular TEAEs by SOC, PT, and maximum severity
- TEAEs by SOC, PT, and maximum relationship
- Ocular TEAEs by SOC, PT, and maximum relationship
- Non-Ocular TEAEs by SOC, PT, and maximum relationship
- Treatment-related TEAEs by SOC and PT
- Ocular Treatment-related TEAEs by SOC and PT
- Non-Ocular Treatment-related TEAEs by SOC and PT
- Serious TEAEs by SOC and PT
- Serious Ocular TEAEs by SOC and PT
- Serious Non-Ocular TEAEs by SOC and PT
- Serious treatment-related TEAEs by SOC and PT
- Serious Ocular treatment-related TEAEs by SOC and PT
- Serious Non-Ocular treatment-related TEAEs by SOC and PT
- TEAEs leading to study withdrawal by SOC and PT
- Ocular TEAEs leading to study withdrawal by SOC and PT
- Non-Ocular TEAEs leading to study withdrawal by SOC and PT
- TEAEs leading to study drug discontinuation by SOC and PT
- Ocular TEAEs leading to study drug discontinuation by SOC and PT
- Non-Ocular TEAEs leading to study drug discontinuation by SOC and PT
- TEAEs leading to death by SOC and PT
- Ocular TEAEs leading to death by SOC and PT
- Non-Ocular TEAEs leading to death by SOC and PT
- TEAEs associated with antimuscarinic function
- Ocular TEAEs associated with antimuscarinic function
- Non-Ocular TEAEs associated with antimuscarinic function
- TEAEs by SOC, PT and Sex
- Ocular TEAEs by SOC, PT and Sex
- Non-Ocular TEAEs by SOC, PT and Sex
- TEAEs by SOC, PT and Race
- Ocular TEAEs by SOC, PT and Race
- Non-Ocular TEAEs by SOC, PT and Race
- TEAEs by SOC, PT and Age
- Ocular TEAEs by SOC, PT and Age
- Non-Ocular TEAEs by SOC, PT and Age

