This document is confidential.

counts should not be displayed and percentages equating to 100% are presented as 100%, without decimal places.

- Tabular display of data for medical history, prior/concomitant medications, and all tabular displays of adverse event data are presented by the body system, treatment class, or SOC with the highest occurrence in the active treatment group in decreasing order, assuming all terms are coded. Within the body system, drug class and SOC, medical history (by preferred term), drugs (by ATC1 code), and adverse events (by preferred term) are displayed in decreasing order. If incidence for more than 1 term is identical, they should then be sorted alphabetically. Missing descriptive statistics or p-values which cannot be estimated are reported as “-”.
- The percentage of subjects is normally calculated as a proportion of the number of subjects assessed in the relevant treatment group (or overall) for the analysis set presented. However, careful consideration is required in many instances due to the complicated nature of selecting the denominator, usually the appropriate number of subjects exposed. Describe details of this in footnotes or programming notes.
- For categorical summaries (number and percentage of subjects) where a subject can be included in more than one category, describe in a footnote or programming note if the subject is included in the summary statistics for all relevant categories or just 1 category and the criteria for selecting the criteria.
- Where a category with a subheading (such as system organ class) has to be split over more than one page, output the subheading followed by “(cont)” at the top of each subsequent page. The overall summary statistics for the subheading should only be output on the first relevant page.

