	14.2.4.7.3.2	Summary of the Change from Stage 2 Baseline in Normalized SER (D) in Stage 2 by Stage 1 to Stage 2 Treatment Description and Visit (Asian vs. Non-Asian)	Stage 2 Intent-to-Treat Set
	14.2.4.7.4.1	Summary of the Change from Stage 2 Baseline in Normalized SER (D) in Stage 2 by Stage 1 to Stage 2 Treatment Description and Visit (Dark Irides vs. Light Irides)	Stage 2 Modified Intent-to-Treat Set
	14.2.4.7.4.2	Summary of the Change from Stage 2 Baseline in Normalized SER (D) in Stage 2 by Stage 1 to Stage 2 Treatment Description and Visit (Dark Irides vs. Light Irides)	Stage 2 Intent-to-Treat Set

This document is confidential.

Header	Table Number	Name	Analysis Set
	14.2.4.7.5.1	Summary of the Change from Stage 2 Baseline in Normalized SER (D) in Stage 2 by Stage 1 to Stage 2 Treatment Description and Visit (U.S. vs. E.U.)	Stage 2 Modified Intent-to-Treat Set
	14.2.4.7.5.2	Summary of the Change from Stage 2 Baseline in Normalized SER (D) in Stage 2 by Stage 1 to Stage 2 Treatment Description and Visit (U.S. vs. E.U.)	Stage 2 Intent-to-Treat Set
	14.2.4.7.6.1	Summary of the Change from Stage 2 Baseline in Normalized SER (D) in Stage 2 by Stage 1 to Stage 2 Treatment Description and Visit (Female vs. Male)	Stage 2 Modified Intent-to-Treat Set
	14.2.4.7.6.2	Summary of the Change from Stage 2 Baseline in Normalized SER (D) in Stage 2 by Stage 1 to Stage 2 Treatment Description and Visit (Female vs. Male)	Stage 2 Intent-to-Treat Set
14.2.4.8		Change from Stage 2 Baseline in Crystalline Lens Thickness (mm) in Stage 2	
	14.2.4.8.1	Summary of the Change from Stage 2 Baseline in Crystalline Lens Thickness (mm) in Stage 2 by Stage 1 to Stage 2 Treatment Description and Visit	Stage 2 Modified Intent-to-Treat Set
	14.2.4.8.2	Summary of the Change from Stage 2 Baseline in Crystalline Lens Thickness (mm) in Stage 2 by Stage 1 to Stage 2 Treatment Description and Visit	Stage 2 Intent-to-Treat Set
14.3		Safety Data Summary Tables	
14.3.1		Adverse Events	
	14.3.1.1.1	Overall Summary of Treatment-Emergent Adverse Events - Stage 1	Stage 1 Safety Set
	14.3.1.1.2	Overall Summary of Treatment-Emergent Adverse Events - Stage 2	Stage 2 Safety Set
	14.3.1.2.1.1	Treatment-Emergent Adverse Events by System Organ Class and Preferred Term - Stage 1	Stage 1 Safety Set
	14.3.1.2.1.2	Ocular Treatment-Emergent Adverse Events by System Organ Class and Preferred Term - Stage 1	Stage 1 Safety Set

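### Stage 1 adverse event tables give crude percentages over on-drug windows of unequal length; if time on drug differs between arms, the arm that stops sooner can look safer, whichever arm that is

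*SAP*

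**What the plan says.** SAP 6.2 counts a Stage 1 treatment-emergent event only if it falls in a window that closes with the child's own treatment: "occur or worsen between the first dose date of Stage 1 and the last dose date of Stage 1". No days are added after the last dose. SAP 9.3 uses the same end point and defines Stage 2 in the same way ("any AE that occurs or worsens between the first dose date of Stage 2 and the last dose date of Stage 2").

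For the tables, SAP 9.3 plans counts of children and "percentage of unique subjects experiencing a TEAE, and total number of events will be tabulated by treatment and Stage". SAP 13.2.5 makes children, not time, the denominator: "The percentage of subjects is normally calculated as a proportion of the number of subjects assessed in the relevant treatment group". The Safety Set (SAP 5.2) admits any child with at least one dose in the stage. The titles under 14.3.1 in SAP 16, of which "Treatment-Emergent Adverse Events by System Organ Class and Preferred Term - Stage 1" is typical, include no rate per person-time and no time to first event.

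Exposure is covered in SAP 9.1 ("Duration of exposure will be summarized using descriptive statistics by treatment group for each stage") and appears in its own tables, 14.1.5.2.x.

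On stopping, the protocol synopsis gives one figure for all arms: "The drop-out rate over the 3 years of the safety and efficacy stage of the study (Stage 1) is estimated to be 27" per cent, or about 10% per year. For a child taken off the drops before the end, the protocol adds: "The subject should continue in the study off study medication". Events that begin after that point can be collected, but they are not treatment-emergent. The output for all adverse events in SAP 9.3 is a listing.

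**The concern.** Stage 1 lasts three years. A child who stops drops after two months adds as much to the denominator as one treated for 36 months, but has far less time in which an event can count. If the arms differ in time on drug, two arms with the same event rate while on drug will show different percentages. The arm with the shorter exposure will show the lower one.

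Safety against Vehicle is part of the primary objective, and the protocol says the arms will be compared on it. These tables are where that comparison will be read. Whether stopping differs by arm will be known only after unmasking, so a measure that allows for it is best specified before then.

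**Working it through.** **The plan's own figure.** Stopping at 10% per year gives 1 − 0.90³ = 27.1% over three years (stated: 27%). For the 0.02% arm, 207 × 0.73 = 151.1 children (stated: at least 150). Both reproduce. The figure is for drop-out from the study. Stopping of drops could be more frequent, because children off drug are asked to stay in.

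**Inputs.** T = 3 years (protocol). Vehicle stopping of 10% per year borrows the plan's drop-out rate. Three things are assumed because the documents give none of them: stopping of 15% or 20% per year on 0.02%; a constant event rate h of 0.02 to 0.20 per year, equal in both arms; and stopping unrelated to events.

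**Formulas.** With annual stopping proportion s, d = −ln(1 − s), so d = 0.105, 0.163 and 0.223 for 10%, 15% and 20%.

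- Mean time on drug = (1 − exp(−3d))/d.
- Crude percentage = h/(h + d) × (1 − exp(−3(h + d))).

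Mean time on drug is 2.57, 2.37 and 2.19 years.

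| h per 100 child-years | Crude %, 10% stop | Crude %, 15% stop (ratio) | Crude %, 20% stop (ratio) |
|---|---|---|---|
| 2 | 5.0 | 4.6 (0.924) | 4.3 (0.852) |
| 10 | 22.4 | 20.8 (0.927) | 19.2 (0.858) |
| 20 | 39.3 | 36.6 (0.931) | 34.0 (0.865) |

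The true ratio is 1.00 in every row. Setting the two crude percentages equal and solving for the rate ratio shows how much excess would be hidden: 1.085 to 1.10 at 15% per year, and 1.18 to 1.22 at 20%.

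**Equal stopping.** With the same d in both arms the ratio is exactly 1.00.

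**Opposite direction.** If Vehicle is the arm that stops at 15% or 20% per year, the ratios invert: 1/0.931 to 1/0.924 = 1.07 to 1.08, or 1/0.865 to 1/0.852 = 1.16 to 1.17. Atropine would then look worse than it is.

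**Early-onset events.** Assume a 20% risk in both arms, all within the first 3 months: h = −ln(0.80)/0.25 = 0.893 per year, then zero.

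- Crude percentage = h/(h + d) × (1 − exp(−0.25(h + d))) = 19.7%, 19.6% and 19.5% for 10%, 15% and 20% stopping. The ratios are 0.99 and 0.99, so the crude table is almost right.
- Child-years to first event or stopping, per child = (1 − exp(−0.25(h + d)))/(h + d) + exp(−0.25(h + d)) × (1 − exp(−2.75d))/d = 2.08, 1.92 and 1.77.
- First-event rate = 9.49, 10.20 and 10.98 per 100 child-years. The ratios are 10.20/9.49 = 1.07 and 10.98/9.49 = 1.16, a false excess in the arm that stops sooner.

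**Kaplan-Meier.** Under these assumptions, cumulative incidence of first event, censored at last dose, estimates 1 − exp(−3h) in the constant-rate case and 20% in the early-onset case, whatever d is. The ratio is 1.00 in both, and simulation agrees.

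**The case against.** Unequal stopping is assumed, not shown. At 15% or 20% per year, 38.6% or 48.8% of the 0.02% arm would stop over three years. If 0.01% matched Vehicle, the 2:2:3 average would be (2 × 27.1 + 2 × 27.1 + 3 × 38.6)/7 = 32%, or 36% with 48.8%, against a planned 27%. This stands as a limit on the size, softened because the 27% is study drop-out.

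A reader might infer that the tables flatter atropine, since children may stop because of its side effects. The documents do not support that. The SAP also lists lack of efficacy among its termination reasons, which could shorten exposure on Vehicle. A child who stops because of an event had that event before the last dose, so it is counted; only later events are lost.

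A reader might also infer that the plan ignores exposure. It does not. Event totals are tabulated, and exposure is summarised by arm over the same first-to-last-dose interval, so events per child-year can be derived as events / (N × mean exposure). Discontinuations are tabulated with reasons. A first-event estimate and its confidence interval cannot be obtained this way, and event totals mix in repeat events.

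The shift is small beside sampling error. It is 0.4 to 2.7 points at 15% per year and 0.7 to 5.3 at 20%. With 138 and 207 children, the 95% half-width is 1.96 × √(p₁(1 − p₁)/138 + p₂(1 − p₂)/207), about 5 to 10 points over the same range. The tables are descriptive, with no test planned. This stands, and it is why the point is an improvement and not a required correction.

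**Conclusion.** The point holds conditionally. The Stage 1 tables use children as denominator over windows of unequal length, and no planned output allows for this in a first-event measure. Distortion needs both unequal time on drug and risk that persists over the three years. Under the assumed stopping and event rates, the percentages in the arm that stops sooner are understated by about 7% to 8% or 13% to 15% in relative terms. With equal stopping the effect is nil, and for events soon after first dose it is close to nil. The direction depends on which arm stops sooner, which no document tells us.

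Two further readings should be set aside. One is that Stage 1 and Stage 2 percentages are not comparable: SAP 9 plans safety tables separately by stage and no comparison between them. The other is that a rate per child-year would be a neutral correction: for early-onset events it misleads where the crude percentage does not.

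**What to change.** Keep the crude percentages and event totals. For Stage 1 overall, ocular, treatment-related and antimuscarinic treatment-emergent events (within 14.3.1.2.1.x, 14.3.1.5.1.x and 14.3.1.11.1.x), add to SAP 9.3 the Kaplan-Meier cumulative incidence of first event by Month 36 in each arm. Time runs from first dose and is censored at the end of the treatment-emergent window. Give the difference from Vehicle with a 95% confidence interval. Specify this before Stage 1 unmasking.

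A first-event rate per 100 child-years may stand beside it, labelled as assuming a roughly constant rate and as able to show a false excess of early-onset events in the arm that stops sooner.

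The cost is a few extra columns, computed from dose and event dates that SAP 9.1 and 9.3 already need. There is no new data collection, and neither the sample size nor the efficacy analysis changes. The added estimate assumes that stopping is unrelated to later event risk, and a footnote should say so.
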